Patients identified as high-risk by the selected tool who survive beyond one year may still warrant palliative care input if their symptom burden is high. The patients enrolled in the validation study will be invited to participate in a consenting longitudinal outcomes study, aiming for at least 50% participation. Symptom burden and functional status will be assessed using the St George's Respiratory Questionnaire (SGRQ),⁽³⁰⁾ Hospital Anxiety and Depression Score (HADS),⁽³¹⁾ Australian modified Karnofsky Score (AKPS),⁽³²⁾ eMRCD score,⁽³³⁾ and modified Borg scale at baseline,⁽³⁴⁾ and 1, 3, 6 and 12 months. The intention is for the baseline and 3 month assessments to be conducted via face to face meetings, and the additional 1, 6 and 12 month assessments to be conducted over the phone; however, in order to maximise the number of participants we will be flexible with home/hospital visits versus telephone interviews according to patient preference. This data will be used both to calculate the relationship between symptom burden and death, and to identify the characteristics of patients who are especially symptomatic.

Inclusion and Exclusion Criteria:

All patients consecutively admitted with ECOPD will be screened.

Inclusion Criteria:

1. Age 35 years or older.
2. Smoking history greater than or equal to 10 pack years.
3. Obstructive spirometry (FEV1/FVC < 0.7).
4. ECOPD primary diagnosis.
5. Survival to discharge.

Exclusion Criteria:

1. Previous inclusion in the study.
2. Malignant neoplasm or other pathology likely to limit survival to less than 1 year.
3. For the longitudinal study only, inability to give informed consent.

Statistical analysis:

The primary outcome of interest is prediction of one year mortality. Assuming a one year mortality rate of 23.2%, (PEARL)⁽³⁾ an area under the receiver operating characteristic (AUROC) curve of 0.70, with a standard error for the AUROC curve of 4%, a minimum sample size of 310 subjects is required (validation cohort).

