The characteristics of the cohort will be summarised using standard descriptive statistics appropriate to the level and distribution of the data. Groups will be compared (including by mortality outcome) using standard tests of statistical inference (e.g. t-test, Mann-Whitney U test, Fishers exact test). The performance of candidate prognostic tools will be compared by 1) assessing the positive and negative predictive value within the high-risk groups; and 2) AUROC curve analysis, with performance compared using the method of DeLong et al. Where data imputation is required, this will be done using multiple imputation methods. Statistical significance will be set at 5% throughout. The statistical analysis plan will be finalised prior to end of recruitment to avoid potential bias.

Outcome Measures:

Validation Study:

Primary outcome:

Positive predictive value and sensitivity of the prognostic tools listed for prediction of one year mortality.*

Secondary Outcomes:

1. Ease of completion of prognostic tools assessed by: a) Likert scale; b) missing data.
2. Area under the receiver operating characteristic curve for each prognostic tool.
3. Negative predictive value of the prognostic tools for prediction of one year mortality.
4. Hospital readmission rates at 30, 90 and 365 days.
5. Proportion of patients on the palliative care register and relation to mortality.
6. Utilisation of palliative care services: hospice; community palliative care team.
7. Inter-observer agreement on scoring.

*This is an exploratory study. The optimal tool to identify patients for advance care planning needs to offer high PPV (i.e. the substantial majority of those identified at high risk of dying should not survive beyond one year) and reasonably high sensitivity (i.e. most deaths within one year should be identified). Ease of completion must also be considered as this will strongly influence engagement.

Longitudinal cohort:

In the whole cohort and individual risk groups within the prognostic tools, assess:

1. Baseline SGRQ, HADS, modified BORG, AKPS.
2. Mean change in SGRQ, HADS, modified BORG, AKPS compared to MCID.
3. Duration SGRQ, HADS, modified BORG, AKPS maintained above baseline.
4. Relation between clinically significant anxiety and depression on discharge and survival, QoL, functional status and readmissions.
5. Best prognostic tool to predict poor QoL and/or death within one year, as per positive predictive value and sensitivity.

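### Longitudinal item 4 words mood at discharge as a yes/no category although graded HADS scores are collected; if only the category is analysed, a cohort of about 155 gives up at least about a third of the information

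*Combined protocol and SAP*

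**What the plan says.** Under Outcome Measures, Longitudinal cohort, item 4 reads "Relation between clinically significant anxiety and depression on discharge and survival, QoL, functional status and readmissions". The list is to be assessed in the whole cohort and within the risk groups of the prognostic tools. Item 4 does not name an instrument, a threshold or a model.

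The Methods paragraph on the longitudinal study lists the "Hospital Anxiety and Depression Score (HADS") among the measures taken at baseline and at 1, 3, 6 and 12 months. It is the only measure of anxiety or depression in the plan. The same paragraph says the data will be used to relate symptom burden to death and mentions no cut. Items 1 and 2 of the longitudinal list use HADS as a baseline level and as a mean change.

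Consent is sought from the validation cohort, "aiming for at least 50% participation". For that cohort, the Statistical analysis section says "a minimum sample size of 310 subjects is required (validation cohort").

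On methods, the same section says "Groups will be compared (including by mortality outcome) using standard tests of statistical inference", with the t-test, Mann-Whitney U test and Fisher's exact test as examples. It adds that the analysis plan will be finalised before recruitment ends.

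**The concern.** A yes/no exposure treats patients just either side of the threshold as opposites, and patients far apart on the same side as identical. When risk or quality of life changes steadily with the score, that wastes information the study has already collected. The cohort is small and deaths are few, so the waste raises the chance of reporting no relation where one exists. The result would also depend on a threshold that the plan does not state.

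A separate gap in definition adds to this. The wording joins anxiety and depression without saying whether a patient needs both, needs either, or is classed once for each. A patient with only one condition has no defined group. This gap does not contribute to the information loss calculated below, but the same rewording closes it.

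**Working it through.** **The plan's own figure.** The only sample size stated is 310, for the validation cohort, with mortality 23.2%, "an area under the receiver operating characteristic (AUROC) curve of 0.70" and a standard error of 4%. The Hanley-McNeil formula is SE² = [A(1−A) + (n₁−1)(Q₁−A²) + (n₂−1)(Q₂−A²)]/(n₁n₂), with Q₁ = A/(2−A) = 0.538 and Q₂ = 2A²/(1+A) = 0.576. At N = 310, n₁ = 71.9 deaths and n₂ = 238.1 survivors, so SE = 0.0376. An SE of 0.04 needs N = 274. The stated 310 is therefore not reproduced, but it errs on the safe side and has no bearing on item 4. No size or power is stated for the longitudinal cohort.

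**Size of the longitudinal cohort.** 0.50 × 310 = 155 patients. This is a floor, because both inputs are minima. Deaths: 155 × 0.232 = 36, assuming that consenters have the mortality assumed for the validation cohort.

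**Information kept after a split.** Assume a standard normal score X, a linear effect, and a fraction p of patients above the cut, at upper normal quantile z. Then Cov(X, indicator) = φ(z) and Var(indicator) = p(1−p). The efficiency relative to the full score is the squared correlation, φ(z)²/[p(1−p)].

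| p above cut | φ(z) | Efficiency | Loss | Equivalent patients (× 155) |
|---|---|---|---|---|
| 50% | 0.3989 | 0.637 | 36% | 99 |
| 30% | 0.3477 | 0.576 | 42% | 89 |
| 20% | 0.2800 | 0.490 | 51% | 76 |
| 10% | 0.1755 | 0.342 | 66% | 53 |

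The last row corresponds to about 16 of 155 patients above the cut.

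**Sensitivity to the shape of the score.** The check was repeated with beta-binomial scores on 0 to 21 (means 6 to 9, SDs 4 to 4.5), cut at 8 or 11. These are illustrative assumptions, not values from the documents. Between 15% and 60% of patients then lie above the cut, the efficiency is 0.528 to 0.682, and the loss is 32% to 47%.

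**What this does to power (two-sided 5%, illustrative effects).**

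- Survival: power = Φ(√(36e)·ln HR − 1.96), where e is the efficiency. For a hazard ratio of 1.6 per SD, the full score (e = 1) gives Φ(6 × 0.470 − 1.96) = 0.805. After a split it is 0.614, 0.571, 0.505 and 0.378 for p = 50%, 30%, 20% and 10%.
- A continuous outcome: power = Φ(√152·atanh(r√e) − 1.96). For r = 0.25 the full score gives 0.883. After a split it is 0.703, 0.658, 0.587 and 0.443.

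The second set assumes that all 155 patients contribute an outcome. At 12 months only about 155 − 36 = 119 would be alive to report quality of life, so absolute power would be lower. Power would also be lower within risk groups.

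**The case against.** The strongest reply is that the plan never specifies a cut. Item 4 is one line in a list of outcomes, it does not name HADS, and the detailed analysis is still to be fixed. This stands in part: a HADS threshold is an inference. It is the natural one, since the wording is categorical and no other mood measure is collected, but a reader should not take it as a stated analysis step.

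A reader might also infer from the sentence on group tests that HADS is to be dichotomised. The documents do not support that. The only grouping the sentence names is mortality outcome, and a t-test or Mann-Whitney test of HADS between patients who died and those who survived would use the whole score. The tests are examples and exclude no model. Moreover, the Methods section plans to relate symptom burden to death with no cut, and items 1 and 2 keep HADS as a score. Any loss is therefore confined to how item 4 is carried out.

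It can also be argued that clinical caseness is a fair question in a study about who may need palliative input. That stands. The category comparison should not be dropped or reduced to mere description. If risk truly steps up at the threshold, the loss calculated above does not apply.

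**Conclusion.** The point holds conditionally and is minor. Item 4 is worded as a category. If it is analysed only that way, the loss is about a third at best for a roughly normal score with a linear effect, and 42% to 51% with 30% to 20% of patients above the cut.

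A reader might take a third to two thirds as a loss fixed by the plan. It is not. The documents give no cut-off and no prevalence, and the upper end is reached only if about 10% of patients lie above the cut. The illustrative HADS-like scores gave 32% to 47%. The figures of 155 patients and about 36 deaths are likewise a target floor and an assumption about consenters.

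Item 4 is a secondary analysis in a study the plan calls exploratory. Neither the primary outcome nor the sample size of 310 is affected.

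**What to change.** In item 4, make the main test of association the relation of the HADS anxiety score and the HADS depression score to survival, QoL, functional status and readmissions. Analyse each score separately as a continuous variable, check for curvature, and report effects per point or per SD. Beside it, report the comparison by clinically significant category for each subscale, with the threshold stated in advance. Treating the subscales separately also settles where a patient with only one condition belongs.

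The change is to the wording of the analysis plan, which is still open. The scores are already collected, so no new data are needed; the cost is a little more analysis.
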